16.1. Registry Discontinuation

Galil reserves the right to terminate the registry at any time. Reasons for terminating may include the following:

- Unsatisfactory enrollment
- Inability to ensure consistent follow-up data collection

18.1. Appendix A: Acronyms and Definitions

Acronym	Definition
AE	Adverse Event
ANC	Absolute Neutrophil Count
BUN	Blood Urea Nitrogen
CBC	Complete Blood Count
CDP	Clinical Discovery Platform
CT	Computed Tomography
CTCAE	Common Terminology Criteria for Adverse Events
EDC	Electronic Data Capture
eCRF	Electronic Case Report Form
eGFR	Estimated Glomerular Filtration Rate
FDA	Food and Drug Administration
FNA	Fine Needle Aspiration
GCP	Good Clinical Practices
HCT	Hematocrit
HIPAA	Health Insurance Portability and Accountability Act
ICF	Informed Consent Form
ICH	International Conference on Harmonization
IRB/IEC	Institutional Review Board/Independent Ethics Committee
LFT	Liver Function Test
MRI	Magnetic Resonance Imaging
PSM	Product Safety Manager
SAE	Serious Adverse Event
SF-12	Short Form 12
TRACE	Tracking Renal Tumors After Cryoablation Evaluation
UADE	Unanticipated Adverse Device Effects

18.2. Appendix B: Anticipated Adverse Event Terms

Adverse Events with the Common Terminology Criteria for Adverse Events
v 3.0 (CTCAE) Short Name

Anticipated Adverse Event(s)	CTCAE Term
Adjacent organ injury/Intra-operative injury	Intraop injury – Select
Allergic reaction/hypersensitivity	Allergic reaction
Angina	Cardiac ischemia/infarction
Arrhythmia	Supraventricular
	Arrhythmia - Select
Atelectasis	Ventricular arrhythmia - Select
	Atelectasis
Bleeding/hemorrhage	Hemorrhage, GI – Select
	Hemorrhage, GU - Select
Cardiac ischemia/myocardial infarction/heart attack	Cardiac ischemia/infarction
Cardiac troponin T (cTnT)	cTnT
Cardiopulmonary arrest, cause unknown (non-fatal)	Cardiopulmonary arrest
Creatinine elevation	Creatinine
Cystitis (requiring intervention)	Cystitis
Death NOS (not otherwise specified)	Death not associated with CTCAE term – Select
Delay/not healing	Wound complication, non-infectious
DVT	Thrombosis/ thrombus/ embolism
Ecchymosis/bruising	Bruising
Edema/swelling	Edema: trunk/genital
Fever (in the absence of neutropenia, where neutropenia is defined as ANC <1.0 x 10 ⁹ /L)	Fever
Fistula, GI	Fistula, GI – Select
Glomerular filtration rate (GFR) elevation	GFR
Hematoma	Hematoma
Hematuria (requiring intervention)	Hemorrhage, GU – Select
Hypertension	Hypertension
Hypotension	Hypotension
Hypothermia	Hypothermia
Ileus	Ileus

Infection (documented clinically) with Grade 3 or 4 ANC	Infection (documented clinically) with Grade 3 or 4 ANC – Select
Infection with normal ANC	Infection with normal ANC – Select
Infection with unknown ANC	Infection with unknown ANC – Select
Infection	Infection – Other (Specify)
Injection site reaction/ extravasation changes	Injection site reaction
Nausea	Nausea
Neuropathy: Motor	Neuropathy-motor
Neuropathy: Sensory (e.g., lumbar radiculopathy)	Neuropathy-sensory
Obstruction, GI (e.g., colon, rectum)	Obstruction, GI – Select
Obstruction, GU (bladder, ureter, urethra)	Obstruction, GU – Select
Pain	Pain – Select
Pelvic vein thrombosis	Thrombosis/thrombus
Perforation, GU	Perforation, GU – Select
Perirenal fluid collection	Leak, GU – Select
Pleural effusion (non-malignant)	Pleural effusion
Pneumothorax	Pneumothorax
Probe site paresthesia (tingling, numbness)	Neuropathy-sensory
Prolonged chest tube drainage or air leak after pulmonary resection	Chest tube drainage or leak
Prolonged intubation after pulmonary resection (>24 hrs after surgery)	Prolonged intubation
Pulmonary embolism	Thrombosis/ thrombus/ embolism
Pulmonary failure/ARDS	ARDS
Pulmonary failure/hypoxia	Hypoxia
Renal artery/renal vein injury	Vascular – Other (Specify)
Renal capsule fracture	Intraop injury – Select
Renal failure	Renal failure
Renal hemorrhage	Hemorrhage, GU – Select
Renal infarct	Renal, other (Specify)
Renal obstruction NOS, GU	Renal, other (Specify)
Renal vein thrombosis	Thrombosis/ thrombus/ embolism
Seroma	Seroma
Skin burn/frostbite	Burn
Stricture of the collection system or ureters/stricture/stenosis	Stricture, anastomotic, GU

Stroke	CNS ischemia
Thrombosis/embolism (vascular access)	Thrombosis/embolism (vascular access)
Thrombosis/thrombus/embolism	Thrombosis/ thrombus/ embolism
TIA (transient ischemic attack)	CNS ischemia
UPJ obstruction	Obstruction, GU-Select
Urinary fistula	Fistula, GU – Select
Urinary renal leakage	Leak GU – Select:
Urinary retention/oliguria	Urinary retention
Vagal reaction	Vasovagal episode
Vomiting	Vomiting
Wound complication (hernia, dehiscence)	Wound complication, non-infectious
Wound infection (abscess, skin infection)	Infection, other

1 LIST OF ABBREVIATIONS AND DEFINITIONS OF TERMS

Table 1: Abbreviations and Definitions of Terms

AE	Adverse event
AKP	Alkaline phosphatase (plasma)
ALP	Alkaline phosphatase (serum)
ALT	Alanine aminotransferase
AP	Anteroposterior
ASA	American Society of Anesthesiologists
AST	Aspartate aminotransferase
BMI	Body mass index
BP	Bodily pain
BUN	Blood urea nitrogen
CC	Craniocaudal
CI	Confidence interval
CKD	Chronic kidney disease
CT	Computed tomography
CTCAE	Common toxicity criteria for adverse events
DSS	Disease-specific survival
eCRF	Electronic case report form
eGFR	Estimated glomerular filtration rate
ENT	Ear nose and throat
FDA	Food and Drug Administration
HCT	Hematocrit
HIV	Human immunodeficiency virus
INR	International normalized ratio
IR	Interventional radiologist
ITT	intent-to-treat
NOTES	Natural orifice transluminal endoscopic surgery
Max	Maximum
MCS	Mental component summary
MDRD	Modification of diet in renal disease
MH	Mental health
Min	Minimum
MRI	Magnetic resonance imaging
NCI	National Cancer Institute
NS	Nephrometry score
OS	Overall survival
QoL	Quality of life
p25	25 th percentile
p75	75 th percentile

PCS	Physical component summary
PF	Physical functioning
PT	Prothrombin time
PTT	Partial thromboplastin time
RCC	Renal cell carcinoma
RE	Role emotional
RP	Role physical
SAE	serious adverse event
SAP	Statistical analysis plan
sCR	Serum creatinine
SD	Standard deviation
SF	Social functioning
TBIL	Total bilirubin
TR	Transverse
TTR	Time to recurrence
UADE	Unanticipated adverse device effect
USA	United States of America
VT	Vitality
WBC	White blood cell

2 INTRODUCTION

Galil Medical's commercially available cryotherapy systems and associated needles are United States of America (USA) Food and Drug Administration (FDA) cleared for use as a cryosurgical tool in the fields of general surgery, dermatology, neurology (including cryoanalgesia), thoracic surgery, ear-nose and throat (ENT), gynecology, oncology, proctology and urology. These systems are designed to destroy tissue in the specialty fields described above by the direct application of temperatures as low as -80°C to -90°C . Cryoablation procedures using Galil's systems may be performed as open, laparoscopic, or percutaneous procedures under imaging guidance: ultrasound, computed tomography (CT) or magnetic resonance imaging (MRI). Thousands of cryoablation procedures have been safely and effectively performed with Galil's cryoablation equipment, primarily for the treatment of prostate and kidney cancers, as well other applications.

3 STUDY OBJECTIVES

The primary objective of the study is to assess the short- and long-term outcomes of patients who undergo renal lesion ablation via cryotherapy with products offered by Galil Medical.

Secondary objectives are:

- Assessment of outcomes across laparoscopic-assisted, percutaneous and open cryoablation procedures.
- Characterization of standards of care for follow-up after cryoablation procedure across the participating registry centers.

4 STUDY DESIGN

4.1 General Design

This is an observational, open-label, single-arm, multi-center study of patients who have undergone renal lesion cryoablation per their physician's standard of care via a Galil Medical cryoablation system using Galil Medical needles.

Data for patients who agree to participate are collected prospectively. (i.e., registry data collection).

TRACE is anticipated to enroll approximately 250 patients at approximately 10 sites.

Patients will be enrolled from a mix of academic and community-based sites.

The schedule and number of follow-up visits for each patient will be determined by his/her physician's standard of care.

Within this context, semi-annual to annual follow-up during the five-year follow-up period is anticipated though it is recognized that follow-up schedules will vary among enrolled patients. Planned per-patient follow-up is 5 years.

The results generated by the registry database will evaluate the use, safety and effectiveness of cryotherapy for renal lesions and will assess the potential advantages and disadvantages of the procedure (e.g., disease recurrence or progression, disease-specific survival rates, overall survival rates, etc).

It will also provide information on long-term surveillance of patients undergoing renal lesion cryoablation.

In addition, this registry may be used as a continuous quality improvement tool on behalf of the treating physicians and will contribute to the development and refinement of standards of care for treatment and follow-up assessments.

4.2 Method of Assignment of Patients to Treatment Groups

Eligible patients at participating sites will be enrolled in this single arm study.

To minimize patient selection bias, participation in the registry is to be offered to all eligible patients on a consecutive basis as they present to the physician at each site.

4.3 Blinding

This is a single arm, open label study, and there is no blinding.

4.4 Determination of Sample Size

Approximately 250 patients are expected to participate in TRACE. As the registry is an observational, non-comparative study, power calculations have not been performed. The estimated sample size has been established to help ensure an adequate population of “completed patients,” defined as those patients completing four or more years of follow-up, at the closure of the registry. This study is not powered for formal statistical analysis.

5 CHANGES IN THE CONDUCT OF THE STUDY OR PLANNED ANALYSES

5.1 Changes in the Conduct of the Study

Patients were enrolled in the following three versions of the study protocol:

- CUC10-RNL02-01 (15Feb2010)
- CUC10-RNL02-02 (28Apr2011)
- CUC10-RNL02-03 (20May2011).

There were no changes that are likely to have an impact on the statistical analysis of the study data.

5.2 Changes in the Planned Analyses

The following are changes from the planned analyses in the current version of the study protocol or in the previous version of the statistical analysis plan (SAP):

- The protocol and previous SAP, listed 'Emergence of new neoplastic disease (any type)' as a study outcome. However, data to assess this outcome was not recorded in the electronic case report form (eCRF) so this outcome cannot be assessed.
- 'Track ablation' was listed in the previous SAP as a procedural/intra-operative endpoint, and this same endpoint was described as 'Galil needle cautery' in the study protocol. However, this data (i.e., needle track ablation/Galil needle cautery) was not recorded in the eCRF so this variable cannot be assessed.
- Method of thaw was listed as having the following 3 options in the SAP: active, FastThaw, and passive. However, FastThaw, which is a type of active thaw, is not included as an option in the current protocol or the eCRF.
- Steering Committee review of draft tables, figures and listings (dated 08May2018) resulted in the following changes
 - In the analysis of time to recurrence, progression will not be considered to be an event of interest
 - AE tables and summaries of renal function will be prepared for both ITT and RCC populations; previously these tables were only prepared for the ITT population
 - Updated tables of post-cryoablation lesion enhancement
 - New table of post-cryoablation lesion enhancement by subgroups of baseline lesion classification (i.e., exophytic, mesophytic, endophytic)

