Key Exclusion Criteria	
 1. Patient is either currently using or has used within the last 30 days an investigational product of any type. 2. Patient has metastatic disease to or from the kidney. 3. Patient has had previous therapy on the index lesion (e.g. radiofrequency, cryoablation, partial nephrectomy).
Renal Lesion Size Criteria	While there are no strict exclusion criteria with regard to lesion size, the typical renal lesion suitable for cryoablation is ≤ 4 cm. Physicians are to use their training and experience to determine the size of a renal lesion that is appropriate for cryoablation.
Statistical Methods	
Continuous variables (e.g., age) will be summarized by the number of subjects, mean, standard deviation, median, minimum and maximum. Categorical variables (e.g., race) will be summarized by frequencies and percentages of subjects in each category.
 
Reporting from the database will include:
 
 • Baseline demographics and disease status will be summarized. • Disease recurrence or progression will be summarized. • Survival and disease-specific survival rates will be summarized at given time points. • Overall survival (time to death) disease-specific survival (time to death of kidney cancer), and recurrence free survival (time to disease recurrence or progression) will be analyzed using the Kaplan-Meier methodology and presented graphically. • Follow-up patterns across physicians/centers will be summarized. • Lesion size reduction will be analyzed. • Relative efficacy in subject subgroups may be explored.

Table of Contents

Protocol Synopsis	iii
Table of Contents	vi
1. Background	1
1.1. Cryotherapy	1
1.2. Cryo-Technology	1
2. Device Description	1
2.1. Cryotherapy Systems	1
3. Registry Rationale	2
4. Registry Objectives	2
5. Registry Design	3
5.1. Description of the Registry	3
6. Registry Population	4
6.1. Subject Enrollment	4
6.2. Inclusion Criteria	4
6.3. Exclusion Criteria	4
6.4. Renal Lesion Size	5
6.5. Withdrawal of Subjects	5
7. Registry Assessments	6
7.1. Pre-Cryoablation Evaluation	7
7.2. Cryoablation Procedure	8
7.3. Early Complications	9
7.4. First Post-Operative Follow-Up	9
7.5. Ongoing Follow-Up Visits	9
7.6. Withdrawal	9
8. Statistical Methods	10
8.1. Sample Size Estimate and Justification	10
8.2. Missing Data	10
8.3. Analysis Populations	10
8.4. Measures	10
8.5. Analyses	12
9. Data Management	13
9.1. Data Collection	13
9.2. Data Processing	13

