8.4. Measures

The parameters that will be analyzed include but may not be limited to the following:

Baseline Assessments

- Demographics
- Baseline characteristics
- Disease status
- Medical History

Procedural Measures

- Procedure method (open, laparoscopic, percutaneous)
- Number of lesions treated with cryoablation
- Type of hemostatic agents or maneuvers used
- Lesion size measured by two methods:
 - 1) 3-dimensional measurements (cm) and
 - 2) Greatest trans-axial diameter (cm)
- Intra-operative biopsy (if available)
- Intra-operative pathology (if available)
- Hospital Stay
- Clinical laboratories (if available)

- Lesion location: anterior, lateral, posterior, upper pole, mid-segment, lower pole, medial, hilar (within 5 mm of the renal hilum), with the following classification of the percentage of the mass that extends into the normal renal parenchymal border⁶
 - Exophytic- <40%
 - Mesophytic- 40-60%
 - Endophytic- more than 60%
- Lesion shape (spherical or non spherical)
- Pathology of the lesion (if available)
- Number and type of cryosurgery needles used
- Number of freeze and thaw cycles
- Freeze and thaw times, per cycle
- Lowest temperature achieved at end of each freeze cycle
- Hilar clamping
- Embolization
- Galil needle cautery
- Method of thaw (active or passive)
- Method of monitoring iceball formation (US, CT, MRI)
- Involvement of the kidney's collecting system
- Post-operative HCT

Safety Measures

- Evaluation of potentially or directly related cryosurgery adverse events

Outcome Measures

- Changes in lesion size reduction measured by two methods:
 - 1) 3-dimensional measurements (cm) and
 - 2) Greatest trans-axial diameter (cm)
- Renal function status as determined by the estimated Glomerular Filtration Rate
- Length of hospital stay
- Post-cryoablation lesion enhancement
- Post-cryoablation biopsy (if performed)
- Disease recurrence or progression as determined locally by an increase in lesion size, contrast enhancement, and/or biopsy
- Disease-specific survival rates
- Overall survival rates and times
- Quality of Life assessment
- Emergence of new neoplastic disease (any type)
- Development of metastatic disease

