8.5. Analyses

Continuous variables (e.g., age) will be summarized by the number of subjects, mean, standard deviation, median, interquartile range, minimum and maximum. Categorical variables (e.g., race) will be summarized by frequencies and percentages of subjects in each category.

Reporting from the database may occur at 6 months and then on an annual basis or more frequently as determined.

Lesion size

Lesion size reduction will be determined by examining the change from baseline at follow-up visits. Method of post-treatment imaging including ultrasound, CT or MRI, use of contrast, enhancement and other imaging parameters will be reported for baseline and follow-up visits.

Renal function status

Renal function status will be determined by examining the estimated Glomerular Filtration Rate (eGFR) at baseline and follow-up visits. The estimated Glomerular Filtration Rate will be calculated using the Modification of Diet in Renal Disease (MDRD) formula.⁵

For creatinine in mg/dL:

$$\text{eGFR} = 175 \times \text{Serum Creatinine}^{-1.154} \times \text{Age}^{-0.203} \times [1.212 \text{ if Black}] \times [0.742 \text{ if Female}]$$

Disease recurrence or progression

Disease recurrence or progression will be determined locally by evidence of an increase in lesion size, contrast enhancement, and/or biopsy.

Disease-specific survival rate is defined as the time in days from cryoprocedure to death due to kidney cancer. Subjects who are alive will be censored at date of their last visit. Subjects who have died from causes other than kidney cancer will be censored at the time of death. Disease-specific survival rates will be summarized by using Kaplan-Meier methodology.

Overall survival rate is defined as the time in days from cryoprocedure to death. Subjects who are alive will be censored at the date of the last visit. Overall survival rates will be summarized by using Kaplan-Meier methodology.

Time to recurrence is defined as the time in days from cryoprocedure to disease recurrence or progression. Subjects without disease recurrence or progression will be censored at the date of their last visit or their date of death (due to any cause). Recurrence free survival rates will be summarized by using Kaplan-Meier methodology.

Intra-operative Data

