6.4.4 Disease recurrence

Time to recurrence (TTR) is defined as the time from date of cryoprocedure to disease recurrence with enhancement in at least one lesion. A lesion is considered to have disease recurrence if the response to the question “What is the status of the lesion?” in the follow-up lesion assessment eCRF page, is “Recurrent”, and there is a “Yes” response to the related question, “If Progressing or recurrent, was the lesion identified by contrast enhancement?”

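### The SAP's time to recurrence counts only contrast-enhancing recurrence, so the protocol's Kaplan-Meier analysis of recurrence or progression is lost and the enhancement requirement is undeclared

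*SAP*

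**What the plan says.** **Protocol.** The synopsis says that "recurrence free survival (time to disease recurrence or progression) will be analyzed using the Kaplan-Meier methodology and presented graphically". Section 8.5 agrees: "Time to recurrence is defined as the time in days from cryoprocedure to disease recurrence or progression". Section 8.4 sets out how the event is established: "Disease recurrence or progression as determined locally by an increase in lesion size, contrast enhancement, and/or biopsy". Enhancement is thus one of three possible routes and is not a condition. On censoring, section 8.5 says: "Subjects without disease recurrence or progression will be censored at the date of their last visit or their date of death".

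**SAP.** Section 6.4 still lists recurrence or progression, judged locally on the same three criteria, as an efficacy endpoint. The time-to-event definition in 6.4.4 is narrower: "Time to recurrence (TTR) is defined as the time from date of cryoprocedure to disease recurrence with enhancement in at least one lesion". To count, the follow-up lesion page must show the status *Recurrent* and a *Yes* to the question on identification by contrast enhancement. Section 8.6.6 has three time-to-event endpoints only: TTR, disease-specific survival and overall survival.

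**Declared changes.** Section 5.2 opens with "The following are changes from the planned analyses in the current version of the study protocol" and adds changes from the previous SAP. Under "Steering Committee review of draft tables, figures and listings (dated 08May2018) resulted in the following changes" it lists "In the analysis of time to recurrence, progression will not be considered to be an event of interest". It gives no reason. Its only entries on enhancement concern the lesion-enhancement tables.

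**The concern.** The time-to-event endpoint was narrowed in two steps, and only the first is declared. Removing progression is stated in 5.2. Requiring enhancement is a second departure from the protocol, and a reader who relies on 5.2 would not learn of it.

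The excluded cases are expected by design. The eCRF asks whether a progressing or recurrent lesion was identified by contrast enhancement, so *No* is a foreseen answer. Follow-up imaging is left to local practice, and the protocol treats use of contrast as something to report, so enhancement may not always be assessed.

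The primary objective is short- and long-term outcome, and both documents name recurrence or progression first among their examples of outcomes. If the only cumulative curve omits some of these failures, it can look more favourable than the analysis the protocol promised, and readers would have no companion estimate to set against it. The declared step also followed review of draft outputs, where an unexplained narrowing most needs the wider definition beside it.

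**Working it through.** The plan gives no figure to reproduce: there is no power calculation, event rate or event count. The check is a comparison of definitions, followed by an illustration on assumed inputs.

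**1. Which cases count**

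| Follow-up lesion status | Identified by enhancement | Event under Protocol 8.5 | TTR event under SAP 6.4.4 |
|---|---|---|---|
| Recurrent | Yes | Yes | Yes |
| Recurrent | No | Yes | No |
| Progressing | Yes | Yes | No |
| Progressing | No | Yes | No |

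The protocol column takes the locally assigned status as the physician's judgement on the three criteria, as SAP 6.4 does.

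**2. Where the excluded cases still appear**

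- SAP 8.6.4 gives enhancing progression per visit. The denominators change from visit to visit, and only the largest lesion is used in patients with several (6.4.2).
- SAP 8.6.9.1 gives lesion status per lesion and per visit.
- SAP 8.8.2 gives disease-free status and new therapy per visit.
- Listings show all data.

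A patient can count at several visits, so these tables cannot be added up to a cumulative patient-level rate.

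**3. Direction**

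Every SAP event is also a protocol event. The number of patients with an event under the SAP is therefore equal to or lower than under the protocol's own rules. Turning this into a statement about Kaplan-Meier rates requires the same censoring for both definitions. As written, the rules differ: the protocol censors at last visit or death, the SAP at last lesion assessment, with extra rules for a missing baseline assessment and for two or more missed visits.

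**4. Illustrative size (all inputs assumed except the planned 250 patients)**

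Let F be the five-year failure rate under the protocol definition and s the share of failures outside the SAP definition. Assume equal censoring and that excluded failures are never counted later. Then

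reported rate = F × (1 − s).

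| F | s = 10% | s = 50% | Events among 250, no dropout |
|---|---|---|---|
| 5% | 5 × 0.9 = 4.5% | 5 × 0.5 = 2.5% | 12.5 become 11.3 to 6.3 |
| 10% | 10 × 0.9 = 9% | 10 × 0.5 = 5% | 25 become 22.5 to 12.5 |
| 20% | 20 × 0.9 = 18% | 20 × 0.5 = 10% | 50 become 45 to 25 |

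A constant-hazard version, event-free (SAP) = event-free (protocol)^(1 − s), agrees closely. For s from 10% to 50%, 95.0% becomes 95.5% to 97.5%, 90.0% becomes 91.0% to 94.9%, and 80.0% becomes 81.8% to 89.4%.

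**5. Sensitivity to censoring**

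Simulation settings: 250 patients, visits at 6, 12, 24, 36, 48 and 60 months, 400 runs per setting, censoring rules 1 and 2 of SAP 8.6.6.1 not modelled.

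- *Same censoring, 0% or 40% dropout:* the SAP-definition failure estimate at 60 months was never above the protocol-definition estimate in any run. At F = 10% and 40% dropout, the means were 8.8% against 9.8% (s = 10%), 8.0% against 10.0% (s = 20%) and 4.9% against 10.0% (s = 50%).
- *Different censoring* (40% dropout, and an assumed 30% of patients whose last image is one visit before their last visit; F = 10%). Here the SAP definition is censored at last image and the protocol definition at last visit:

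| s | SAP definition | Protocol definition | Runs with SAP higher |
|---|---|---|---|
| 0 | 11.1% | 10.1% | – |
| 10% | 10.1% | 10.2% | 52% |
| 20% | 8.8% | 10.0% | 16% |
| 50% | 5.4% | 9.8% | none |

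The censoring difference alone can raise the estimate and hide a small exclusion. The two definitions are comparable only under one set of rules.

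**The case against.** The strongest reply is that most of this is open and within the rules. Removal of progression is declared. Protocol 8.3 leaves analysis detail to the SAP, and Protocol 15.1 lets the Steering Committee recommend analyses. The enhancement condition is written plainly in 6.4.2 and 6.4.4. It also fits the technical-success table in 6.5.1, which counts a progressing or recurrent but non-enhancing lesion as a success when cryotherapy was completed. That looks like a deliberate convention. It may come from the previous SAP, which is not available. The registry is single-arm and not powered for formal testing, no success threshold rests on TTR, and progression remains in descriptive tables.

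All of this is fair, and it rules out any suggestion that results drove the change. It does not restore the cumulative estimate. A convention inherited from an earlier SAP is still a change from the current protocol, which 5.2 says it covers.

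Three narrower objections also have force:

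- **Censoring.** Read with the 6.4.4 definition and with Appendix 2, which censors everyone without an event, rule 3 of 8.6.6.1 probably does apply to excluded failures. It is worded for patients established to be free of recurrence, so only the censoring date needs clarifying. A *Recurrent* lesion with the enhancement answer missing is also unaddressed.
- **Direction.** Under the two documents' differing censoring rules, the direction of the difference in rates is not established. Only the inequality in event counts is.
- **The proposed wider curve.** Based on eCRF status and SAP censoring, it makes the protocol definition operational but does not copy it exactly. A biopsy-positive lesion recorded as stable would be missed. Since SAP 6.4 ties the physician's judgement to the protocol criteria, using status is reasonable.

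**Conclusion.** The concern holds. Followed as written, the SAP produces no cumulative patient-level estimate of recurrence or progression, although the protocol promises one and SAP 6.4 still lists the endpoint. The enhancement requirement for TTR is missing from 5.2, and the declared removal of progression carries no reason.

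The size cannot be known from the documents. The illustrative reduction runs from half a percentage point (5% reported as 4.5%) to ten points (20% reported as 10%). It rests on assumed failure rates, assumed excluded shares, equal censoring, and no later enhancing recurrence in the excluded patients. The gap shrinks if some of them later show enhancing recurrence. The change should be made; the narrower TTR can stay as an additional analysis.

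**What to change.** 1. **Add the wider analysis.** Present Kaplan-Meier rates and curves for the first *Progressing* or *Recurrent* status in any treated lesion, however identified, in the ITT and RCC populations, beside the enhancing-recurrence TTR. Apply the 8.6.6.1 censoring rules to both. Note one caveat: under rule 2, a first progression after two missed visits is censored in the wider curve, while a later enhancing recurrence in the same patient could still count in the narrower one. Repeating the Cox models is optional.
2. **Complete 5.2.** Declare the enhancement requirement for TTR, and give the reason and timing for both changes.
3. **Clarify 8.6.6.1, rule 3.** State the censoring date in the narrowed TTR for patients with progression or non-enhancing recurrence, and say how a *Recurrent* lesion with no enhancement answer is handled.

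The cost is one extra set of Kaplan-Meier outputs per population from existing eCRF fields, plus short text edits. The reported rate may look less favourable.
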